6.1 Safety Analysis Set

The safety analysis set will consist of all subjects who receive at least one dose of investigational product.

6.2 Pharmacokinetic (PK) Analysis Set

The PK analysis set will consist of all subjects for whom at least one PK parameter or endpoint can be adequately estimated.

6.3 Pharmacodynamic (PD) Analysis Set

The PD analysis set will consist of all subjects for whom at least one PD parameter or endpoint can be adequately estimated.

6.4 Primary Analysis set

The primary analysis set will consist of all subjects from cohort 1 to 6 who receive at least one dose of investigational product.

6.5 Final Analysis set

The final analysis set will consist of all subjects from cohort 7 who receive at least one dose of investigational product.

7. Planned Analyses

7.1 Interim Analysis and Early Stopping Guidelines

DLRM members will oversee progress of the study and make recommendations relating to early closure / extension or alteration of the study based on ongoing monitoring of the study data. Refer to Section 7.4.1 and 7.4.2 of the protocol amendment 3 for further details.

7.2 Primary Analysis

The primary analysis will occur after all subjects from cohorts 1 to 6 have completed the study and it will include all subjects from cohorts 1 to 6.

Data from cohort 1 to 6 will be locked prior to primary analysis is carried out and clean snapshot data from cohort 1 to 6 will be used for primary analysis.

7.3 Final Analysis

The final analysis will occur after all subjects in cohort 7 have completed the study and it will include all subjects from cohort 7.

Data from cohort 7 will be locked prior to final analysis and clean snapshot data from cohort 7 will be used for final analysis.

8. Data Screening and Acceptance

8.1 General Principles

The objective of the data screening is to assess the quantity, quality, and statistical characteristics of the data relative to the requirements of the planned analyses.

8.2 Data Handling and Electronic Transfer of Data

The Amgen Global Study Operations-Data Management (GSO-DM) department will provide all data to be used in the planned analyses. This study will use the RAVE database.

8.3 Handling of Missing and Incomplete Data

The frequency of missing and incomplete data is expected to be low in this study and therefore, missing data will not be imputed.

Laboratory measurements that are below the quantification limits will be considered equal to the lower limit of quantification (LLQ) for the calculation of population averages as a part of the summary tables. There will be no imputation of clinical laboratory values below LLQ for individual subject level data in line listings.

Biomarker data that are below the quantification limits will be considered equal to half of the LLQ for all analyses unless specified otherwise.

PK concentrations that are below the quantification limits will be set to zero when engaging non-compartmental model to compute PK parameters.

For partial dates (such as treatment emergent AE, concomitant medication, drug administration etc.), imputation of dates will be carried out as per Appendix A.

8.4 Detection of Bias

Lack of protocol compliance and the potential for biased statistical analyses will be examined by listing important protocol deviations (IPD) by cohort and site. The clinical study team will identify and document the criteria for important protocol deviations.

8.5 Outliers

Details of detecting outliers can be found in the Data Management Plan (DMP) or other data management document. In addition, outliers may be identified via the use of descriptive statistics. All confirmed outlier data will be included in the analyses presented in this statistical analysis plan unless there is sufficient scientific justification to exclude them.

Pharmacokinetic (PK) plasma concentration data will be evaluated for outliers by visual inspection, and decisions to re-assay individual samples will be made in accordance with standard pharmacokinetic evaluation practice.

8.6 Distributional Characteristics

Where appropriate, the assumptions underlying the proposed statistical methodologies will be assessed.

8.7 Validation of Statistical Analyses

Programs will be developed and maintained, and output will be verified in accordance with current risk-based quality control procedures.

Tables, figures, and listings will be produced with validated standard macro programs where standard macros can produce the specified outputs.

The production environment for statistical analyses consists of Amgen-supported versions of statistical analysis software; for example, the SAS System version [9.4] or later.

9. Statistical Methods of Analysis

9.1 General Considerations

Descriptive statistics will be provided for selected demographics, safety, PK and PD endpoints. Descriptive statistics on continuous measurements will include means, medians, standard deviations and ranges, while categorical data will be summarized using frequency counts and percentages. Data will be presented and summarized by treatment at each time point, as applicable. Graphical summaries of the data may also be presented.

Data for subjects receiving placebo will be combined across cohorts 1, 3 and 5 (monotherapy cohorts) and separately across cohorts 2, 4 and 6 (combination therapy cohorts). Placebo data for subjects in cohort 7 will not be combined with other cohorts.

Data for subjects receiving AMG 598 will be presented separately by cohort.

When data are summarized by time, the values recorded against the scheduled time points listed in the protocol will be used. When assessing minimum/maximum increases or decreases over the study, all assessments, including unscheduled assessments will be used.

9.2 Subject Accountability

A summary of subject disposition and investigational and non-investigational product administration will be provided for all subjects enrolled in the study along with a summary of sites.

A summary of study reporting and analysis set dispositions will also be prepared. A subject disposition listing, noting inclusion in each analysis subset, will be provided for all subjects enrolled.

A subject listing noting duration of investigational product administration, reason for discontinuation of treatment, and reason for discontinuing study will be provided. A list of subjects screened but not enrolled (screen failures) will be provided.

A subject listing will be provided for randomization information, randomized treatment and actual treatments, including usage of liraglutide, as applicable.

9.3 Important Protocol Deviations

Important Protocol Deviations (IPDs) categories are defined by the study team before the first subject's initial visit and updated during the IPD reviews throughout the study prior to database lock. These definitions of IPD categories, subcategory codes, and descriptions will be used during the course of the study. Eligibility deviations are defined in the protocol. Listings of subjects with IPDs as well as those with inclusion and exclusion deviations will be provided separately.

9.4 Demographic and Baseline Characteristics

Demographic (ie. age, age groups [< 40, >= 40], sex, race, ethnicity) and baseline characteristics (height, weight, body mass index, medical history) will be summarized by cohort and treatment received and overall (i.e. total from all the cohorts involved in the analysis and irrespective of treatment received) using descriptive statistics. If multiple

races have been reported for a subject, the subject will be categorized as multiple race as well as by the combination of race.

9.5 Efficacy Analyses

This section is not applicable.

9.6 Safety Analyses

9.6.1 Analyses of Primary Safety Endpoint(s)

The primary objective of this phase 1b study is to evaluate the safety and tolerability of AMG 598 administered alone or in combination with liraglutide in subjects with obesity. The safety analyses will include the descriptive summary of treatment emergent adverse events, laboratory data, vital signs, physical measurements and ECG data.

9.6.2 Adverse Events

The Medical Dictionary for Regulatory Activities (MedDRA) version 20.1 or later will be used to code all events categorized as adverse events to a system organ class and a preferred term. The severity of each adverse event will be graded using the clinical severity grading system provided in Appendix B.

The subject incidence of adverse events will be summarized for all treatment-emergent adverse events, serious adverse events (SAE), adverse events leading to withdrawal of investigational product (AMG598 or Placebo) and/or non-investigational product (Liraglutide), fatal adverse events and adverse events of interest (EOI).

Subject incidence of all treatment-emergent adverse events, serious adverse events, adverse events leading to withdrawal of investigational product (AMG598 or Placebo) and/or non-investigational product (Liraglutide), fatal adverse events and adverse events of interest (EOI) will be tabulated by system organ class and preferred term (in which system organ class will be ordered alphabetically and the preferred terms within each system organ class will appear in descending order of frequency).

In addition, summaries of treatment-emergent and serious adverse events by preferred term in any treatment arm will be provided in descending order of frequency.

Summaries of treatment-emergent and serious adverse events will also be tabulated by system organ class, preferred term, and grade.

The subject incidence of treatment-emergent adverse events will be summarized by actual treatment received.

Treatment related treatment emergent adverse events will be further summarized (by system organ class and preferred term) for AMG 598 and liraglutide separately.

Subject incidence of events of interest will also be summarized according to their categories and preferred term. Events of interest of hypersensitivity will be identified using a narrow search/scope in standardized MedDRA query (SMQ). Events of interest of osteoporosis/osteopenia, gastrointestinal nonspecific inflammation and dysfunctional conditions, hyperglycaemia/new onset diabetes mellitus, depression and suicide/self-injury, and peripheral neuropathy will be identified using a broad search/scope in SMQ. Immunogenicity and Injection site reactions will be identified using Amgen-defined MedDRA search strategies.

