9.2.3.1 Adverse Events

9.2.3.1.1 Time Period and Frequency for Collecting and Reporting Safety Event Information

9.2.3.1.1.1 Adverse Events

The adverse event grading scale to be used for this study will be the Clinical Adverse Event Severity Grading Scale and is described in Section 12.4.

The investigator is responsible for ensuring that all adverse events observed by the investigator or reported by the subject that occur after the first dose of AMG 598/placebo through the end of study are reported using the Event CRF.

9.2.3.1.1.2 Serious Adverse Events

The investigator is responsible for ensuring that all serious adverse events observed by the investigator or reported by the subject that occur after the informed consent through end of study are reported using the Event CRF. All serious adverse events will be collected, recorded and reported to the sponsor or designee within 24 hours, as indicated in Section 12.4. The investigator will submit any updated serious adverse event data to the sponsor within 24 hours of it being available.

9.2.3.1.1.3 Serious Adverse Events After the Protocol-required Reporting Period

There is no requirement to monitor study subjects for serious adverse events following the protocol-required reporting period or after end of study. However, these serious adverse events can be reported to Amgen. Per local requirements in some countries, investigators are required to report serious adverse events that they become aware of after end of study. If serious adverse events are reported, the investigator is to report them to Amgen within 24 hours following the investigator's knowledge of the event.

Serious adverse events reported outside of the protocol-required reporting period will be captured within the safety database as clinical trial cases and handled accordingly based on relationship to investigational product.

The method of recording, evaluating, and assessing causality of adverse events and serious adverse events and the procedures for completing and transmitting serious adverse event reports are provided in Section 12.4.

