10.3.2.3 Safety Analyses

10.3.2.3.1 Analyses of Primary Safety Endpoint(s)

Endpoint	Statistical Analysis Methods		
Primary	Subject incidence of treatment-emergent adverse events including fatal		
	adverse events, serious adverse events, adverse events leading to		
	withdrawal from investigational product or other protocol-required		
	therapies, and significant treatment emergent adverse events.		
	Summary statistics of safety laboratory test results including summary		
	statistics at each protocol scheduled visit by cohort / combined placebo		
	cohort.		
	Summary statistics of vital signs including summary statistics at each		
	protocol scheduled visit by cohort / combined placebo cohort.		
	Summaries over time and/or changes from baseline over time will be		
	provided for all ECG parameters.		
	Summary statistics from mental health questionnaires.		

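### SAP 9.6.2 does not say that its SAE and event-of-interest tables exclude events before the first randomised dose, and in cohort 7 the SAP's TEAE definition literally admits run-in events

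*SAP*

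**What the plan says.** **Collection.** Protocol 9.2.3.1.1.2 requires reporting of "all serious adverse events observed by the investigator or reported by the subject that occur after the informed consent through end of study". For adverse events in general, Protocol 9.2.3.1.1.1 covers only those "reported by the subject that occur after the first dose of AMG 598/placebo through the end of study are reported using the Event CRF". SAEs are therefore the one class with a planned collection period before dosing.

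**Tabulation.** SAP 9.6.2 opens with "The subject incidence of adverse events will be summarized for all treatment-emergent adverse events, serious adverse events (SAE), adverse events leading to withdrawal", followed by fatal events and events of interest. It repeats that list for the tables by system organ class and preferred term, and adds "Summaries of treatment-emergent and serious adverse events will also be tabulated by system organ class, preferred term, and grade". Only one sentence ties a summary to treatment received: "The subject incidence of treatment-emergent adverse events will be summarized by actual treatment received".

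**Protocol analysis text.** Protocol 10.3.2.3.1 describes the primary safety analysis as "Subject incidence of treatment-emergent adverse events including fatal" events and then serious ones, which makes SAEs a subset of TEAEs. Protocol 10.3.2.3.2 instead names SAE tables and TEAE tables as separate items. SAP Section 10 declares no departure from the protocol.

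**Definitions.** SAP Section 5 defines a TEAE as beginning or worsening after the initial dose of investigational product, identified by a CRF flag. It defines investigational product as AMG 598 or placebo. All cohort 7 subjects receive placebo on day -28 as run-in (Protocol 5.1; Table 2-3) and are randomised on day 1 (Protocol 7.2). The protocol safety set requires a dose on day 1 (10.2.1.1). The SAP version (6.1) omits the day.

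**The concern.** SAE incidence is part of the primary safety endpoint. An SAE during screening or run-in cannot be an effect of AMG 598, yet the SAP text allows it to appear in an AMG 598 or placebo column. The safety analysis set does not prevent this, because it selects subjects and not event dates.

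There are two separate gaps:

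- **Screening SAEs, all cohorts.** The SAE tables carry no stated onset limit. Two competent programmers could produce different SAE tables from the same data.
- **Run-in SAEs, cohort 7.** Even a programmer who applies the SAP's treatment-emergent rule could keep them, because the run-in placebo is literally a dose of investigational product.

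With 30 subjects per arm in cohort 7 and six per AMG 598 group in cohorts 1-6, a single wrongly placed event is visible.

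**Working it through.** The plan states no figure that bears on this point, so there is none to reproduce. The check is a reading of the rules followed by a bound on their effect.

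**1. How the rules treat three SAEs in a cohort 7 subject who is later dosed**

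| Onset | SAE table, read literally | SAE table with the SAP's TEAE filter | Anchored on first randomised dose |
|---|---|---|---|
| Day -40 (screening) | counted | not counted | not counted |
| Day -20 (after run-in placebo) | counted | counted, because onset follows a placebo dose | not counted |
| Day 10 | counted | counted | counted |

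The first row is the ambiguity in SAP 9.6.2. The second row is the defect in SAP Section 5. In cohorts 1-6 only the first kind of event can arise, because there is no run-in dose.

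**2. Length of the window before day 1** (Protocol 5.3.2)

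- Cohort 7: 28 days of screening + 28 of run-in = 56, out of 56 + 207 = 263 days. 56/263 = 21.3%, of which run-in is 28/263 = 10.6%.
- Cohorts 1-6: 28/(28 + 207) = 28/235 = 11.9%.

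**3. Effect of one event**

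- Cohort 7 arm: 1/30 = 3.3 percentage points.
- One AMG 598 group in cohorts 1-6: 1/6 = 16.7 percentage points.

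**4. Expected number of affected subjects**

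The documents give no SAE rate for this trial. Assume a risk r of 2% to 5% per 207 days at a constant hazard, h = -ln(1 - r)/207. This gives h = 0.0000976 per day at r = 2% and 0.000248 at r = 5%.

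| Quantity | Formula | r = 2% | r = 5% |
|---|---|---|---|
| Cohort 7, all 56 days | 60 × (1 - exp(-56h)) | 0.33 | 0.83 |
| Cohort 7, run-in only | 60 × (1 - exp(-28h)) | 0.16 | 0.41 |
| Cohorts 1-6 together | 48 × (1 - exp(-28h)) | 0.13 | 0.33 |
| One six-subject AMG 598 group | 6 × (1 - exp(-28h)) | 0.016 | 0.041 |

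The chance of at least one such subject in cohort 7 is 1 - exp(-60 × 56h), or 28% to 57%. For the assumed rates these are upper bounds, because some of these subjects would be removed before dosing.

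**The case against.** **The text may already intend a restriction.** SAP 9.6.1 introduces the adverse event analysis as a summary of treatment-emergent events, Protocol 10.3.2.3.1 nests SAEs in TEAEs, and the SAP declares no change. The phrase in "Summaries of treatment-emergent and serious adverse events will also be tabulated by system organ class, preferred term, and grade" can be read as events that are both. No sentence says how a pre-dose SAE is assigned to an arm. Much of this stands, and it is why the screening part is an ambiguity. It does not close the matter. Read as events that are both, that sentence would leave the SAP with no TEAE table by grade. That reading also cannot apply to the comma-separated lists, where SAEs are their own item. SAP 9.1 summarises data by treatment, so SAE tables by arm are planned.

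**The SAP did not depart from the protocol.** A reader might infer an undeclared change. The documents do not support that: Protocol 10.3.2.3.2 uses the same loose list, so the inconsistency begins within the protocol.

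**Day 1 is clear from context.** Protocol 9.1.2 dates day 1 in cohort 7 from the first dose after randomisation, and sites may complete the CRF flag on that basis. This is a fair reading of intent, but SAP Section 5 does not say it. That section also equates enrolment with randomisation and schedules it on day -28 for cohort 7, against day 1 in Protocol 7.2.

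**Few events would qualify.** Cohorts 1-6 must be otherwise healthy (criterion 104). Cohort 7 must show no change in eligibility on day 1 (criterion 112), and an adverse event is a listed reason for removal from run-in (Protocol 8.2.1). The first-in-human study had reported no SAEs in 56 subjects, blinded and still ongoing. All of this stands and limits the size. Removal in run-in is not automatic, however, and cohort 7 admits chronic stable conditions.

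**The consequence is limited.** Analyses are descriptive, onset dates are recorded, and the treatment-related tables are already restricted to treatment-emergent events. This also stands for screening SAEs. For run-in SAEs, that restriction relies on the same TEAE definition.

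**Conclusion.** The point holds as a clarification worth making before database lock. For screening SAEs the SAP is ambiguous: they could be counted by arm, but the documents do not establish that they would be. For run-in SAEs in cohort 7 the problem survives a treatment-emergent filter, because the stated definitions literally make those events treatment-emergent.

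Two stronger conclusions would be wrong. A reader might infer that a day -20 SAE in cohort 7 would appear in the SAE table but not in the TEAE table. On the SAP's literal definitions it enters both. A reader might also infer a bias for or against AMG 598. Events before randomised treatment do not systematically favour either arm, so the harm is chance misattribution.

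The size is small: fewer than one affected subject expected in cohort 7 (0.33 to 0.83) and in cohorts 1-6 together (0.13 to 0.33). These figures rest on an assumed 2-5% risk and a constant hazard. One event would add 3.3 points to a cohort 7 arm. The 16.7-point shift in a six-subject group is possible but unlikely.

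**What to change.** 1. **SAP Section 5:** define treatment-emergent as onset or worsening after the first randomised dose of AMG 598/placebo (day 1), and state that the cohort 7 run-in placebo does not count. Confirm that the CRF flag uses the same dose; if not, derive the status from recorded onset dates.
2. **SAP 9.6.2:** write *treatment-emergent serious adverse events* in every by-treatment summary, and put the same limit on the event-of-interest tables.
3. **SAP 6.1:** restore the day 1 requirement so that the safety analysis set matches Protocol 10.2.1.1.
4. **New listing:** show SAEs with onset between informed consent and the first randomised dose, not attributed to an arm.

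The cost is a few words, one filter and one listing, with no change to data collection. The downside is that pre-dose SAEs appear only in a listing.

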9.6.3 Laboratory Test Results

Individual chemistry, hematology and urinalysis laboratory data listings will be reviewed. Parameters that will be collected are presented in table A below.

Values outside the normal laboratory reference range will be flagged as high or low at baseline and each post-baseline time point on the listings.

For the parameters that are bolded in below Table A, summary statistics including actual value, change from baseline and percent change from baseline at protocol defined visits will be summarized.

				Central
Local		Local	I s s s I I s b s u s t s m s	
Laboratory:		Laboratory:	Local Laboratory:	Laboratory:
Chemistry	Local Laboratory:	Urinalysis	Hematology	Other
Sodium	Drug Screen	Specific	RBC	
Potassium	Benzodiazepines	gravity	Hemoglobin	Safety
Chloride	Barbiturates	рН	Hematocrit	assessments
Bicarbonate/CO	Opiates	Blood	MCV	P1NP
2	Tetrahydrocanna	Protein	МСН	CTX-1
Total protein	binol	Glucose	МСНС	
Albumin	Cocaine	Bilirubin	Platelets	Lipid Panel
Calcium	Amphetamines	WBC	WBC	Cholesterol
Glucose	Ethanol (may be	RBC	Differential	(total)
BUN or Urea	performed by a	Epithelial cells	Total	LDL-C
Creatinine	breath test)	Bacteria	Neutrophils -or-	HDL-C
Total bilirubin		Casts	seg. Neutrophils	Triglycerides
Direct bilirubin	Viral Panel	Crystals	and Bands/Stabs	
ALP	Hep B surface		 Eosinophils 	
AST (SGOT)	antigen		 Basophils 	
ALT (SGPT)	HBcAb		 Lymphocytes 	
TSH – screening	HepCAb		 Monocytes 	
only	HCV RNA			
Calcitonin –	PCR(as			

Table A:

		Lagal		Central
Local		Local		• • • • • • • •
Laboratory:		Laboratory:	Local Laboratory:	Laboratory:
Chemistry	Local Laboratory:	Urinalysis	Hematology	Other
screening only	necessary)		Coagulation	
Tryptase (in the	HIV ^a		PT/INR	
event of a suspected anaphylactic reaction) Amylase Lipase	Reproductive Serum or Urine Pregnancy FSH		PTT/APTT	

^a HIV assessment is recommended.

ALP = alkaline phosphatase; ALT alanine aminotransferase; AST = aspartate aminotransferase; BUN = blood urea nitrogen; CTX-1 = C-terminal telopeptides of Type I collagen; GIP = Glucose dependent insulinotropic peptide; GLP-1 = Glucagon-like peptide-1; HbA1c = ; hemoglobin A1c; HDL = high density lipoprotein; Hep = hepatitis; HIV = human immunodeficiency virus; HLA = human leukocyte antigen; INR = international normalized ratio; LDH = lactate dehydrogenase; LDL = low density lipoprotein; MCH = mean corpuscular hemoglobin; MCHC = mean corpuscular hemoglobin concentration; MCV = mean corpuscular volume; P1NP = Procollagen Type 1 N-Terminal Peptide; PT = prothrombin time; PTT/APTT = activated partial thromboplastin time; RBC = red blood cell count; RDW = Red cell distribution width; SGOT = serum glutamic-oxaloacetic transaminase; SGPT - serum glutamic-pyruvic transaminase; WBC = white blood cell count

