10.3.2.3.3 Laboratory Test Results

Hematology, chemistry and urinalysis data will be listed and reviewed for each subject. Values outside the normal laboratory reference range will be flagged as high or low on the listings. Depending on the size and scope of changes in laboratory data, summaries of laboratory data over time and/or changes from baseline over time may be provided.

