9.6.6 Electrocardiogram

All on-study ECG data listings will be reviewed.

Each ECG will include the following measurements: QRS, QT, QTc, RR, and PR intervals. The Fridericia's (QTcF) QT correction and Bazett's (QTcB) QT correction will be computed as specified in section 5. All ECG parameters will be summarized over time and change from baseline over time will be provided.

Further, subjects' maximum change from baseline in QTcF and QTcB will be categorized in following categories and the number and percentage of subjects in each group will be summarized. Unscheduled assessments will be included in the determination of the maximum change.

- ≤ 30 msec
- > 30 60 msec
- > 60 msec

Subjects' maximum post baseline values in QTcF and QTcB will also be categorized in the following categories and the number and percentage of subjects in each group will be summarized.

- ≤ 450 msec
- > 450 480 msec
- > 480 500 msec
- > 500 msec

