Appendix B. Reference Values/Clinical Severity grading

The clinical severity grading scale is as follows:

- grade 1 = mild (e.g., asymptomatic or mild symptoms, clinical or diagnostic observations only, intervention not indicated, or does not interfere with activity)
- grade 2 = moderate (e.g., minimal intervention indicated or interferes with activity)
- grade 3 = severe (e.g., medically significant but not immediately lifethreatening, prevents daily activity, or requires treatment)
- grade 4 = life-threatening (i.e., refers to an event in which the subject was, in the view of the investigator, at risk of death at the time of the event)
- grade 5 = fatal

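### SAP 9.6.3 plans no count of subjects by maximum liver value in multiples of ULN, and the liver retests the protocol requires enter no laboratory table

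*SAP*

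**What the plan says.** Protocol 4.1 and SAP 2.1 make safety laboratory data part of the primary endpoint. SAP 9.6.3 plans listings with values flagged high or low and, for the tests in bold in its Table A, "summary statistics including actual value, change from baseline and percent change from baseline at protocol defined visits will be summarized". It plans no shift table, no count by multiple of ULN and no maximum.

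Two sentences in SAP 9.1 decide which values enter which output. For by-visit tables: "When data are summarized by time, the values recorded against the scheduled time points listed in the protocol will be used". For extremes: "When assessing minimum/maximum increases or decreases over the study, all assessments, including unscheduled assessments will be used". The second sentence needs a planned minimum or maximum output to act on. Only SAP 9.6.6 supplies one, for QTcF and QTcB, in categories: "Unscheduled assessments will be included in the determination of the maximum change".

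The protocol leaves room for more. Section 10.3.2.3.1 promises "Summary statistics of safety laboratory test results including summary" statistics by visit, and 10.3.2.3.3 says that "summaries of laboratory data over time and/or changes from baseline over time may be provided". The SAP adds nothing beyond the by-visit statistics.

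Protocol 12.7 sets liver thresholds in multiples of ULN (Table 12-2). Section 12.7.1 requires close observation when ALT or AST exceeds 3 x ULN, or doubles from an already raised baseline. That brings a repeat liver panel with INR within 24 hours, and daily retests while bilirubin exceeds 2 x ULN or INR exceeds 1.5.

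**The concern.** The retests that 12.7.1 requires are unscheduled by nature. Under the SAP 9.1 rule they appear in listings but in no laboratory table. A peak first seen on a retest is therefore missing from every laboratory summary. By-visit means and ranges also cannot show how many different subjects crossed a threshold at any time.

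The adverse event tables close only part of this gap. An isolated rise that prompts no treatment or change of therapy is, under protocol 9.2.4 and 12.4, largely left to the investigator's view of clinical significance. If it is recorded, its grade does not give the multiple of ULN: SAP Appendix B describes grade 1 as, for example, "asymptomatic or mild symptoms, clinical or diagnostic observations only, intervention not indicated, or does not interfere with activity", so symptom-free ALT of 4 and of 7 x ULN can both be grade 1. The broad-search events of interest in SAP 9.6.2 end with "hyperglycaemia/new onset diabetes mellitus, depression and suicide/self-injury, and peripheral neuropathy will be identified using a broad search/scope in SMQ", and neither that list nor the rest of the section names a hepatic category.

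At stake is a per-arm count at the level where the protocol itself calls for close observation. It matters most in cohort 7, the only sizeable controlled comparison.

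**Working it through.** **1. The plan's own figure.** The plan gives none for liver values. The nearest is the detection chance in SAP 3.2 for 66 subjects on AMG 598: 1 - 0.95^66 = 0.966 and 1 - 0.90^66 = 0.999. Both reproduce. They concern adverse events, so they do not carry over to a liver rise that is never recorded as one.

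**2. Where each kind of rise is counted** (protocol Table 12-2, 12.7.1, 9.2.4, 12.4):

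- ALT/AST >3 x ULN with bilirubin >2 x ULN or INR >1.5, subject to the baseline and alternative-cause conditions: reported as a serious adverse event, so counted.
- Any rise that leads to withholding: a change of therapy, so an adverse event, so counted.
- Isolated symptom-free ALT/AST >3 to 5 x ULN, or between 5 and 8 x ULN for under 2 weeks with monitoring kept up: close observation applies, but no Table 12-2 criterion is met. CRF capture is required for potential liver injury; entry in the adverse event tables is not assured.
- Isolated total bilirubin >2 to 3 x ULN: no Table 12-2 criterion is met, because that table needs >3 alone, or >2 together with ALT/AST >3. Entry in the adverse event tables is not assured.

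The last two groups are the residual gap.

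**3. Can by-visit statistics supply the count?** As read from Table 2-3, cohort 7 has five post-baseline chemistry visits (days 29, 57, 85, 145, 207). Assume 30 subjects with ALT at 0.5 x ULN, including at baseline, except for one value of 4 x ULN on each of days 29, 57 and 85. At each of those visits:

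- mean = (29 x 0.5 + 4)/30 = 0.617
- median = 0.5
- SD = 3.5/sqrt(30) = 0.639
- range = 0.5 to 4.0
- mean change from baseline = 3.5/30 = 0.117

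These hold whether one subject is raised three times or three subjects once each. The counts above 3 x ULN, with exact 95% intervals, differ:

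- one subject: 1/30 = 3.3% (0.1 to 17.2%)
- three subjects: 3/30 = 10.0% (2.1 to 26.5%)

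With one such value at each of the five visits, the count could be anything from 1/30 to 5/30 = 16.7% (5.6 to 34.7%).

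**4. The retest peak.** If one of these subjects has a 24-hour retest at 5.6 x ULN, the by-visit range still ends at 4.0. The count above 5 x ULN should be 1/30.

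**5. Is a case likely?** If the true rate of a maximum ALT above 3 x ULN is 2%, 5% or 10% (assumed; the documents give none), the chance of at least one such subject among 30 is 1 - 0.98^30 = 45%, 1 - 0.95^30 = 79% or 1 - 0.90^30 = 96%.

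**The case against.** The strongest reply is that nothing is hidden and little changes. Listings show every value. A raised value at a scheduled visit shows in that visit's range, if the test is among those summarised, and sends the reader to the listing. The SAP matches the protocol, the analyses are descriptive, and hepatotoxicity is not among the key risks in protocol 3.3.3. Bilirubin rises in animals were minimal, transient and non-adverse (3.3.3.1). Subject safety rests on 12.7 and, in cohort 7, on review by the medical monitor and the Safety Surveillance Team (7.4.2.1), not on a report table. The example in the working is constructed, and its intervals overlap heavily. All of this stands. It limits the importance of the point but does not supply the count.

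Three stronger readings are tempting and are not supported.

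- A reader might infer that isolated rises are counted nowhere. Section 12.7.1 closes by requiring potential liver injury events and the related laboratory results to be entered in the CRFs, and elsewhere names the Event CRF as an example. Such cases may therefore reach the adverse event tables. The wording does not settle which form applies, so neither a count nor its absence can be asserted.
- A reader might take INR as the clearest case, since coagulation appears to be scheduled at screening only. But a post-baseline INR arises mainly from retests triggered by ALT/AST above 3 x ULN or by withholding, and most such cases are already serious or other adverse events. Little remains.
- A reader might argue that the entry caps (1.5 x ULN in cohorts 1 to 6, 2 x ULN in cohort 7) make any value above 3 x ULN a real change. Criterion 203 applies at screening only, which in cohort 7 is days -56 to -29, and the Part 2 criteria (6.3, 6.4) set no liver limit. A subject could be above 3 x ULN on day 1, and from 2 x ULN the crossing is only a 1.5-fold rise. The added table therefore needs to handle baseline.

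**Conclusion.** The point holds as a reporting gap in part of the primary endpoint. The liver retests required by protocol 12.7.1 enter no planned laboratory table. The planned by-visit statistics cannot give the number of subjects per arm whose maximum exceeded a given multiple of ULN. What remains uncounted with any reliability is isolated ALT/AST above 3 x ULN and isolated total bilirubin above 2 and up to 3 x ULN. In the worked example the same output fits 1/30 and 3/30 over three visits, and up to 5/30 over five.

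The example's ALT values and the 2%, 5% and 10% rates are assumptions. Visit days are read from a schedule table that is broken in the text available here. Bold type is lost there too, so which tests are summarised cannot be confirmed; no choice of tests would create a maximum or a count. The practical gain lies mainly in cohort 7, and the point implies no failure of subject protection.

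**What to change.** Add one table to SAP 9.6.3, by cohort and treatment, with placebo pooled as in SAP 9.1. It should give the number and percentage of subjects by maximum post-baseline value, scheduled and unscheduled, in multiples of the reporting laboratory's ULN:

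- ALT/AST >3, >5 and >8
- total bilirubin >2 and >3
- ALP >8
- ALT/AST >3 with total bilirubin >2, or with INR >1.5 where measured (show the number with an INR)
- ALT/AST rise of 2-fold or more over an elevated baseline, to match the second trigger in 12.7.1

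Count a threshold only if it was not already exceeded at baseline, or cross baseline category with maximum post-baseline category. Define baseline as the last value before the first dose after randomisation, which in cohort 7 is the day 1 pre-dose sample. Label the table as biochemical thresholds, not Table 12-2 stopping criteria, because those also depend on duration, symptoms, baseline and alternative causes.

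The cost is one table from data already collected, using the SAP's own rule for maxima and its QTc layout. In cohorts 1 to 6, with 8 subjects each, it partly repeats the listings. Trial conduct does not change, and the open wording in protocol 10.3.2.3 already allows it.
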